3. OBJECTIVES

3.1. PRIMARY OBJECTIVE

To assess the impact of surgery on quality of life, specifically patients' role functioning derived by the EORTC QLQ-C30 at one year after resection of symptomatic pineal cyst. Role functioning reflects activities in daily life, which is a higher-order outcome than symptoms, i.e. both symptoms and treatment have an impact on the level of functioning, a clear picture of the functioning of the patient. Role functioning was also the most relevant issue to patients seen in the clinic and the members of Pineal Cyst UK.

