4. PROJECT PLAN

We propose a single-centre, prospective controlled cohort study. Unlike previously published studies, which were retrospective cohort studies, this cohort will have a priori defined enrolment criteria, data points, outcomes and is powered to answer the study's questions. Given the patient numbers required (N=40) it is feasible to carry out the study in a single centre. The main advantages this design are maximum homogeneity of the study's variables and simplicity of its execution. However, if there is interest from other UK untints the study will be expanded under strict conditions of adherence to the study protocol and subject to governance approvals. This would accelerate recruitment.

As a result of Amendment 1, 21 consecutive patients who underwent an operation during the 5-year period prior to the commencement of the study (i.e. since 1st January 2016) and completed the required questionnaires and consented to participating in the study will be included in the total number of 40 surgically treated patients.

The primary outcome will be assessed once 40 surgically treated patients reach 12-months follow up. Since all the data required to assess the primary outcome was collected as a part of clinical care and will be available if patients consent for this to be used in the study, it may only be necessary to recruit 19 patients since the commencement of the study in order to achieve the primary objective as well as secondary objectives 3.2.1. and 3.2.2. of the study.

We will analyse and publish the result of the study with N=40. At that point, the cohort will consist of patients who underwent surgery before and after the commencement of the study. We will also evaluate the available data pertaining to the rest of the secondary of objectives (3.2.3, 3.2.4) and exploratory objectives (3.3.1 and 3.3.2). These data will be less complete and results less informative, but we believe this is a practically and ethically beneficial compromise to mitigate the negative impact of the COVID-19 pandemic.

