4.4.1. Primary outcome and sample size

The primary efficacy outcome measure is the change of role functioning scale of the EORTC QLQ c30 questionnaire at 12 months after surgery.

It is anticipated that a considerable clinical effect will be achieved, that is, an improvement of at least 20 points in a 0-100 scale in the role functioning scale. Using the estimated standard deviation of 42 at pre-surgery (retrospectively assessed) and 18 at 6 months post-surgery (prospectively assessed)(Fedorko, Zweckberger and Unterberg, 2018), with a conservative assumption of the correlation coefficient between pre- and post-surgery scores being 0.5, the estimated standard deviation of the difference between pre and post-surgery is 36. With a 5% significance level, 90% power, 37 participants are required to detect the 20 points using a paired t-test.

Allowing for some non-compliance and to maximise the yield from the secondary outcome measures we aim to recruit 40 participants. The assumptions used for sample size estimation will be monitored by the Study Steering Committee (see below). The conservatively treated patients, i.e. those who chose not to undergo surgery, will be recruited until the completion of surgically-treated patients. No power calculations are required as outcome measures related to the conservatively treated (non-surgery) cohort are among secondary objectives of this study.

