4.4.4. Statistical analyses

The paired t-test will be applied to the primary efficacy analysis for all patients received surgery treatment. A detailed statistical analysis plan will be drafted prior to any analyses performed.

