Nevins, E. J. et al. (2016) 'Incidental Pineal Cysts: Is Surveillance Necessary?', World neurosurgery, 90, pp. 96–102. doi: 10.1016/j.wneu.2016.02.092.

4. EORTC-QLQ-C30 Questionnaires

EORTC QLQ-C30 (version 3)

We are interested in some things about you and your health. Please answer all of the questions yourself by circling the number that best applies to you. There are no "right" or "wrong" answers. The information that you provide will remain strictly confidential.

Please fill in your initials:	
Your birthdate (Day, Month, Year):	
Today's date (Day, Month, Year):	31

		Not at	A Little	Quite a Bit	Very Much
1.	Do you have any trouble doing strenuous activities, like carrying a heavy shopping bag or a suitcase?	1	2	3	4
2.	Do you have any trouble taking a long walk?	1	2	3	4
3.	Do you have any trouble taking a short walk outside of the house?	1	2	3	4
4.	Do you need to stay in bed or a chair during the day?	1	2	3	4
5.	Do you need help with eating, dressing, washing yourself or using the toilet?	1	2	3	4

Du	ring the past week:	Not at All	A Little	Quite a Bit	Very Much
6.	Were you limited in doing either your work or other daily activities?	1	2	3	4
7.	Were you limited in pursuing your hobbies or other leisure time activities?	1	2	3	4
8.	Were you short of breath?	1	2	3	4
9.	Have you had pain?	1	2	3	4
10.	Did you need to rest?	1	2	3	4
11.	Have you had trouble sleeping?	1	2	3	4
12.	Have you felt weak?	1	2	3	4
13.	Have you lacked appetite?	1	2	3	4
14.	Have you felt nauseated?	1	2	3	4
15.	Have you vomited?	1	2	3	4
16.	Have you been constipated?	1	2	3	4

During the past we	eek:				1	Not at All	A Little	Quite a Bit	Very Much
17. Have you had diarrh	ea?					1	2	3	4
18. Were you tired?						1	2	3	4
19. Did pain interfere w	ith your daily a	activities?				1	2	3	4
20. Have you had difficultike reading a newsp						1	2	3	4
21. Did you feel tense?						1	2	3	4
22. Did you worry?						1	2	3	4
23. Did you feel irritable	e?					1	2	3	4
24. Did you feel depress	sed?					1	2	3	4
25. Have you had difficu	ulty rememberi	ng things?		\		1	2	3	4
	26. Has your physical condition or medical treatment interfered with your family life? 1 2 3 4							4	
27. Has your physical cointerfered with your			nt			1	2	3	4
28. Has your physical co- caused you financial		dical treatme	nt			1	2	3	4
For the following best applies to you 29. How would you rate					umber	bet	ween	1 and	7 that
2	3	4	5	6	7				
Very poor	Y				Excel	lent			

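### The primary before-after estimate cannot separate surgery from pandemic restrictions that start or end between a patient's two questionnaires

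*Supplement*

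**What the plan says.** Section 4.4.1 defines the endpoint: "The primary efficacy outcome measure is the change of role functioning scale of the EORTC QLQ c30 questionnaire at 12 months after surgery". Section 3.1 explains the choice: "Role functioning reflects activities in daily life, which is a higher-order outcome than symptoms". The only analysis named, in section 4.4.4, is: "The paired t-test will be applied to the primary efficacy analysis for all patients received surgery treatment". A detailed analysis plan is promised there but is not among the documents.

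The QLQ-C30 is reproduced after the reference list. Item 6 asks "Were you limited in doing either your work or other daily activities" and item 7 asks "Were you limited in pursuing your hobbies or other leisure time activities", both with a one-week recall and four response levels. Neither asks for a reason. The form has a field for the date of completion.

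Under Amendment 1 (synopsis and section 4), 21 consecutive patients operated on since 1 January 2016, a window described as five years, count towards the 40, leaving about 19 to recruit after commencement. Section 4 calls this a "practically and ethically beneficial compromise to mitigate the negative impact of the COVID-19 pandemic". Section 4.5.1 of the same version, dated June 2021, treats the pandemic as current. Everywhere the pandemic appears, it is a matter of recruitment and face-to-face contact, never something that could move the outcome score.

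**The concern.** A one-sample paired test attributes to the operation everything that changed, on average, between the two forms. That is a problem when an outside event with a date acts on the quantity being measured. A closed workplace or leisure venue can be recorded on items 6 and 7 as a limitation even if the patient's health is unchanged.

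The effect depends on where a patient's two forms fall:

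- both before the pandemic: no effect;
- first form before restrictions, 12-month form during them: improvement is hidden;
- first form during restrictions, 12-month form after them: improvement appears without any contribution from surgery;
- both during restrictions: roughly no effect, if restrictions were similar at both times.

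The second pattern can arise mainly among past patients and the third mainly among new ones. The pooled estimate could therefore shift in either direction, and a difference between past and new patients could be misread as a difference in surgical benefit. Section 4.4.4 treats all pairs alike.

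**Working it through.** **1. The plan's own figure.** Section 4.4.1 uses an "estimated standard deviation of 42 at pre-surgery (retrospectively assessed) and 18 at 6 months post-surgery (prospectively assessed", and a correlation of 0.5.

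SD of change = √(42² + 18² − 2 × 0.5 × 42 × 18) = √1332 = 36.5 (the plan gives 36). A two-sided paired t-test at 5% for 20 points with 90% power needs n = 37 by the noncentral t, with either SD. The stated 37 reproduces, so the issue is bias and not sample-size arithmetic.

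**2. Inputs not in the documents (assumptions).**
- Role functioning is items 6 and 7, scored linearly to 0-100. One category on one item is then 100/6 = 16.7 points.
- Restrictions lower the score by d = 10 or 15 points on average, which is less than one category on one item.
- Restrictions began in March 2020, and the 21 past operations are spread evenly over the five-year window. Operations in the 12 months before restrictions began number 21 × 12/60 = 4.2. These patients are taken to have the first form outside and the 12-month form inside restrictions.
- Of the 19 new patients, k have the first form inside and the 12-month form outside; k can be 0 to 19.
- All other pairs are on the same side.

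**3. Pooled bias at n = 40:** (k − 4.2) × d / 40.

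| k | d = 10 | d = 15 |
|---|---|---|
| 0 | −1.05 | −1.58 |
| 4 | −0.05 | −0.08 |
| 10 | +1.45 | +2.18 |
| 17 | +3.20 | +4.80 |
| 18 | +3.45 | +5.18 |
| 19 | +3.70 | +5.55 |

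The largest value, 5.55, is 28% of the 20-point target. The mid-range values (k = 4 to 10) lie between about 0 and 2 points, at most 2.18/20 = 11% of it.

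**4. Effect on the test.** With n = 40, SD 36.5 and 39 degrees of freedom, the noncentrality is bias × √40 / 36.5. If surgery had no effect, the two-sided rejection probability would be:

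| Bias | Noncentrality | P(p < 0.05) |
|---|---|---|
| 0 | 0 | 5.0% |
| 1.45 | 0.25 | 5.7% |
| 2.18 | 0.38 | 6.6% |
| 5.0 | 0.87 | 13.5% |
| 5.55 | 0.96 | 15.5% |

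In the other direction, a bias of −1.58 with a true 20-point effect (mean 18.42) lowers power at n = 40 from 92.2% to 87.6%.

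**5. What this calculation leaves out.**
- Floor: section 4.1 admits only symptom category B, and the background section reports that two thirds of patients could not keep up normal activities or work. Patients already near the worst score cannot lose another 10 to 15 points, so positive biases shrink.
- Form dates: section 4.5.2 puts the first form at diagnosis, but the count of 4.2 treats it as completed at operation. The gap is not given. A longer gap would let restrictions begin inside more past pairs.
- Past patients operated on after restrictions began are counted as same-side. Any whose 12-month form came after restrictions ended would add to the positive side.

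**The case against.** The strongest reply is that calendar covariates and sensitivity analyses belong in the analysis plan, which section 4.4.4 promises before any analysis and which is not shown. Nothing is lost meanwhile, because each form already carries its date. Much of this stands: the absence of such detail from a protocol would not by itself be a fault. But the protocol itself fixes the primary test. It also pools patients across the pandemic without recognising anywhere that the outcome could respond to it. The past patients' forms were already filled in during clinical care (section 5), so the period rule should be written down before those data are analysed.

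A second reply is that this is only the usual history threat of an uncontrolled before-after study, and that the background section already says a randomised trial is likely to be needed. That is fair as to the design. This threat, however, is specific and dated, and it can be partly checked within the operated patients at almost no cost.

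A third reply is that the size is assumed. That stands in full. The documents give no restriction dates, form dates or effect of restrictions on the score.

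A reader might infer that restrictions affect every patient's change score. The documents do not support this: pairs completed wholly before the pandemic are untouched, and patients at the floor cannot worsen. A reader might also take 13.5% as the expected false-positive rate. It needs a 5-point bias, which cannot occur at d = 10 in this calculation (maximum 3.70). At d = 15 it needs at least 18 of the 19 new patients to have restrictions end between their forms.

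**Conclusion.** The concern holds in a limited form. The stated primary analysis cannot distinguish the effect of surgery from restrictions that started or ended between forms, and the pooled sample contains pairs where either may have happened. Net direction and size are unknown. Under the assumptions above, the bias runs from −1.6 to +5.6 points, with mid-range values of about 0 to 2 points and rejection probabilities of roughly 5 to 7% when surgery does nothing. The upper end is a near-worst case that ignores floor effects.

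A reader might conclude that the primary result will be inflated or that the paired t-test must be replaced. Neither follows. The patterns push in opposite directions and may partly cancel, and a true effect of the anticipated size, "an improvement of at least 20 points in a 0-100 scale in the role functioning scale", would be larger than any bias in this range. What is at stake is mainly how exactly the estimate can be attributed to surgery, and how a past-versus-new difference is read. The change is worth making because it costs so little; it is not a reason to doubt the whole study.

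**What to change.** Keep the paired t-test as the primary analysis and add the following to section 4.4.4, before any analysis:

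1. **Flag.** Mark each QLQ-C30, from its completion date, as filled in while public restrictions applied or not. Fix the restriction dates in advance.
2. **Same-side estimate.** Report the mean change with its confidence interval in pairs with both forms on the same side of the flag. Report the change by pattern as well: both outside, restrictions started, both inside, restrictions ended.
3. **Adjusted model.** Fit one repeated-measures model over all visits with the flag as a time-varying covariate. Conservative patients' forms may inform the calendar effect only for the months they cover. They are recruited alongside the study, so they cannot inform the change from before the pandemic into it among the past surgical patients, and section 4 expects these data to be less complete.
4. **Reporting.** Show these results beside the primary estimate. If the adjusted estimate differs materially, by a margin written down beforehand, qualify the conclusion about the impact of surgery. The additional analyses should not act as a veto through an undefined requirement that they agree.

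The cost is a few lines of text and one variable derived from forms already collected. The downside is precision: the same-side estimate uses fewer pairs and will have a wider interval, so it should be read as a check on the primary result and not as a second test.

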4.5. STUDY PROCEDURES

Individual patient participation – overview (see also Flow Chart and Flow Table):

4.5.1. Screening

- a. Patients referred to neurosurgical clinic that are diagnosed with symptomatic pineal cyst (SPC) will be screened against inclusion and exclusion criteria. The treatment will be offered and carried out as per current evidence-based clinical practise. Whether patients chose surgery or conservative management, they will be eligible to be enrolled in the study.
- b. Information about the study will be provided to eligible patients by a member of the research team after the end of the first neurosurgery clinic appointment. This can occur face-to-face or over the telephone.
- c. Informed consent to participate in the study will be obtained by a member of the research team after the patients have considered the relevant information about participation. Online completion of consent forms will be considered, in keeping with the reduction of face-to-face appointments due to the pandemic. Paper consent forms will also be available.

As a result of Amendment 1, patients who had undergone resection of the pineal cyst prior to commencement of the study and have completed symptoms and quality of life questionnaires will be contacted via telephone by a member of the research team. All patients are currently under follow up. The study and their potential role as participants in the study will be explained and if patients express their interest in participating in the study. Patient Information Sheet and Consent Form will be send to them. They will be offered an appointment to discuss this in person or, if they prefer, they can sign the consent form in the presence of a witness and mail this back to the research team.

4.5.2. Symptoms and QoL questionnaires (see Appendices 1-4)

a. Patients who chose surgical treatment

Study participants will undergo surgery as per normal clinical pathway. The participants will be asked to fill in symptom and quality of life (QoL) questionnaires at the entry to the study

(at diagnosis) and at 3, 12, 26 and 36 months after surgery. The participants will be given the options of filling the questionnaire on the paper or on-line.

b. Patients who chose conservative management

The participants will be asked to fill in symptom and quality of life (QoL) questionnaires at the entry to the study (at diagnosis) and at 3, 12, 26 and 36 months after the diagnosis. The participants will be given the options of filling the questionnaire on the paper or on-line.

Once enrolled patients will participate in the study for 3 years, although each participant will be able to leave the study at any time without giving a reason. This will in no way affect their clinical management. This includes the option for patients to choose to undergo surgery at any time even if they have initially elected to pursue conservative management.

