	2. Assessment of symptoms at 1 year and also at 2 and 3 years after					
	surgery.					
	3. Assessment of all aspects of quality of life and symptoms in patients					
	who did not undergo surgery (= conservative management) at the time					
	of diagnosis and at 1, 2 and 3 years after joining the study; and					
	investigation the differences at baseline and follow up between those					
	treated surgically and conservatively.					
	4. Comparison of objective neuropsychological assessments before the					
	operation and at 1 year after surgery.					
	5. Development of a model to identify anatomical (based in MRI scans)					
	and clinical (symptoms) predictors of improvement of QoL after surgery					
	for SPC					
Study design	Prospective observational cohort study					

Date and Version No: 28/06/2021 Version 1.2

Interventions No interventions. This is an observational study.	
---	--

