3.2. SECONDARY OBJECTIVES

3.2.1. Quality of Life – before and after surgery

We will determine the probability of improvement of overall QoL as well as each individual domain, as defined by the EORTC QLQ-C30 questionnaire (Appendix 1). This will be done by comparing pre-operative and post-operative assessments at 3, 12, 24 and 36 months following resection of SPC.

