3.2.3. Quality of life and symptoms of patients treated conservatively

We will assess Quality of Life and Symptoms of patient who chose conservative management at enrolment and at 3, 12, 24 and 36 months following the diagnosis of SPC. These data will also serve to compare baseline Quality of Life and Symptoms between patients managed surgically and conservatively. We will explore the differences of outcomes of patients who

choose conservative and surgical treatments with adjusting confounding factors. This cohort will also give us an idea about changes in severity of symptoms and QoL over time.

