4.3. RECRUITMENT STRATEGY AND SCREENING

When patient receive a diagnosis of a symptomatic pineal cyst (SPC) during a routine neurosurgical clinic consultation at the Addenbrooke's Hospital in Cambridge they will be informed about the possibility of taking part in this study by the patient clinical care team.

Patients referred to neurosurgical clinic for evaluation of their pineal cyst, either symptomatic or asymptomatic will be seen as per current practice. If a diagnosis of a symptomatic pineal cyst (SPC) is made (SPC > 9mm, Eide and Ringstad symptom B category), patients will be screened against inclusion and exclusion criteria (see Section 4.1 and 4.2). If fulfilling the entry criteria, patients will be offered participation in the study. Patients will be advised about the aims, expected benefits and risks of surgery as per current practice. Patients who request surgery will undergo an operation as per existing care pathway. Patients who chose not to undergo surgery will pursue conservative management as per existing care pathway. Interested patients regardless the pathway they have chosen will be explained the study and will be given a Participant Information Sheet (PIS). If they wish to join the study they will sign a Consent Form for participation in the study.

We anticipate that recruitment of the required number of patients treated by surgery will take approximately two years (N=40). The follow up for the primary outcome measure will take additional year. The study specific follow up assessments will be performed at one year after surgery for the primary efficacy outcome measure and SPC-related symptoms review. Given the relatively low burden posed by administering and filling in of the of the questionnaires, one early (3 months following surgery) and two late (at 2 and 3 years after surgery) surveys of symptom control and QoL will be performed (see also attached Flow Chart – Appendix 7 and Flow Table – Appendix 8).

Eligible participants who chose not to undergo surgery (this is an entirely clinical and not a research-related decision) will be recruited the non-surgery (conservative treatment) cohort (see also attached Flow Chart – Appendix 7 and Flow Table – Appendix 8). This is to

investigate/explore the QoL difference between surgery and non-surgery patients, both at diagnosis (baseline) and 3, 12, 24 and 36 months after treatment (one of the secondary objectives).

4. 4. NUMBERS AND METHODS OF ANALYSIS.

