30. How would you rate	e your overall	quality of life	e during th	e past wee	ek?				
1 2	3	4	5	6	7				
Very poor					Excel	lent			

5. Study-specific questionnaire – preoperative

Pineal Cyst Questionnaire – BEFORE OPERATION

The information that you provide will remain strictly confidential.

Are yo	ou currently at work/school?	yes	no	
	If no, when did you last work?			
	What is your job?			
	Is it full time or part time job?	yes	no	
	If you are off work, is this because o	f the symរុ	otoms you came to	see me with?
		yes	no	

Weight

- now kg
- 1 year ago kg (approximately if not known precisely)
- 5 years ago or before symptoms started kg (approximately if not known precisely)

Do you think that there has been a relationship between weight and symptoms (presence of the symptoms or their severity)? yes no If yes, please, describe.

Medications

	Name	Started*	Stopped*
HRT			
Contraceptive pill			
Hormonal supplements			
Vitamins			
Painkillers			

^{*}Approximate date when you started and stopped taking this medication.

Have you had glandular fever	(= infectious mononucleosis)
------------------------------	------------------------------

yes no

Headache

Do you suffer from more than one type of headache (that are different in nature)? Please describe.

yes no

Do you suffer from migraines?

yes no

Do you have constant headache, i.e. headache that is there all the time and never really goes

away? yes no

If yes, when did it start?yearsmonths ago

Where in the head is your 'main headache'? (tick whichever apply to you)

Behind the eye – Left/Right

Behind the eyes

Between the eyes

On the back of the head

It is like a tight belt

On top of the head

In the centre of the head

Other (please describe)

Which word best describes your 'main headache'?

Sharp

Like a tight belt/band

Like a knife

Pulsating

Burning

Other (please describe)

When did the 'main headache' start?

Please give an approximate date

Please give an event, if there is one, that the headaches relate to

Did you 'main headache' start before my migraine headaches? yes no n/a

Does anything trigger your 'main headache'?

Sound/noise

Looking up

Light

Other (please describe)

What makes your 'main headache' worse?

Lying flat

Sitting up

Working on a computer

Any light

Fluorescent light

Noise

Other (list as many causes as you want)

When is your 'main headache' worst?

In the morning

In the evening

Any other time

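### The surgical baseline is taken at diagnosis while follow-up runs from surgery, so any change during the wait enters the primary paired difference and misaligns the cohort comparison

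*Supplement*

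**What the plan says.** All references are to protocol version 1.2.

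- **Surgical patients, section 4.5.2a:** forms at study entry, "at diagnosis) and at 3, 12, 26 and 36 months after surgery".
- **Conservative patients, section 4.5.2b:** forms at study entry, "at diagnosis) and at 3, 12, 26 and 36 months after the diagnosis".
- **Objective 3.2.1:** the analysis is to be made by "comparing pre-operative and post-operative assessments at 3, 12, 24 and 36 months following resection of SPC". No time before surgery is attached to the pre-operative assessment.
- **Preoperative symptom form:** headed "Pineal Cyst Questionnaire – BEFORE OPERATION", with no completion window.
- **Section 4.3, cohort comparison:** "both at diagnosis (baseline) and 3, 12, 24 and 36 months after treatment", covering both cohorts.
- **Conservative follow-up elsewhere:** the synopsis has "of diagnosis and at 1, 2 and 3 years after joining the study"; section 3.2.3 has "conservative management at enrolment and at 3, 12, 24 and 36 months following the diagnosis of SPC".

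The primary outcome (4.4.1) is the change in QLQ-C30 role functioning at 12 months after surgery. It is tested by a paired t-test in all operated patients (4.4.4). Under Amendment 1, 21 of the 40 surgical patients were operated on before the study began. They contribute forms already completed in clinical care (section 4 and section 5), and the timing of those forms relative to surgery is not given.

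**The concern.** A paired change score attributes to surgery everything that happens between the two measurements. Here the first is fixed to diagnosis and the second to 12 months after the operation, so the difference spans the wait for surgery as well as the post-operative year. Surgery follows the normal clinical pathway. Nothing in the text shown limits the wait, repeats the questionnaire before the operation or adjusts for the interval.

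The role-functioning items ask about the past week, so a score at diagnosis describes that week and not the patient's state going into surgery. The change while waiting could go either way. Entry requires a symptom score of at least 5, so some regression towards improvement is plausible, which would flatter surgery. Worsening while waiting is also possible and would hide part of a real benefit. The primary test has no control group to remove either.

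A second, lesser consequence falls on the exploratory comparison of the cohorts. They share a baseline event, but follow-up is counted from surgery in one and from diagnosis in the other, so scores with the same label lie at different distances from baseline.

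**Working it through.** **1. The plan's own figure.** Section 4.4.1 gives standard deviations of 42 before and 18 after surgery, correlation 0.5, target 20 points, 5% significance and 90% power.

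SD of the difference = √(42² + 18² − 2 × 0.5 × 42 × 18) = √(1764 + 324 − 756) = √1332 = 36.5 (the plan states 36).

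The exact two-sided paired t-test needs N = 37 with either value: power at 37 is 90.8% with SD 36 and 90.0% with SD 36.5. At n = 40 it is 93% and 92%. The stated 37 reproduces, and nothing here disputes it.

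**2. What the primary difference contains.** Let D be the mean change in role functioning from the baseline form to surgery, and S the mean change from surgery to 12 months after it.

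Expected paired difference = D + S.

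Only S belongs to the period after the operation. The documents give neither the wait nor D, so the values below are assumptions.

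**3. Size relative to the 20-point target.**

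| Assumed drift per affected patient | All 40 affected | Only the 19 prospective patients affected |
|---|---|---|
| 5 points | 5/20 = 25% | 5 × 19/40 = 2.375; 2.375/20 ≈ 12% |
| 10 points | 10/20 = 50% | 10 × 19/40 = 4.75; 4.75/20 ≈ 24% |

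**4. Effect on the test** (n = 40, SD 36, two-sided 5%). Probability of rejection when S = 0 and patients improve while waiting:

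| Drift | All 40 affected | Only 19 affected |
|---|---|---|
| 0 | 5% | 5% |
| 5 | 14% | 7% |
| 10 | 40% | 13% |

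In the other direction, if all patients worsen by 5 or 10 points while waiting, a true gain of 20 is measured as 15 or 10, and power falls from 93% to 73% or 40%.

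**5. Cohort comparison.** Time from baseline to the 12-month score is wait + 12 months in surgical patients and 12 months in conservative patients. With assumed waits of 3 to 12 months, that is 15 to 24 months against 12.

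**6. Correlation.** A longer interval might lower the correlation between the two scores. At 0.4 the SD of the difference is √(2088 − 604.8) = 38.5 and power at n = 40 is 89%. At 0.3 it is √(2088 − 453.6) = 40.4 and power is 86%. This effect is small beside the possible bias.

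**The case against.** Several stronger readings are tempting, and the documents do not support them.

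- **That the baseline is not pre-operative.** It is: diagnosis precedes the operation, and objective 3.2.1 and the form's heading are consistent with that. The gap is the absence of a fixed point shortly before surgery.
- **That the primary result is biased in favour of surgery, or by a known amount.** No wait, drift or direction is given. The pandemic is cited for the amendment and for fewer face-to-face visits, never for waiting times.
- **That all 40 patients carry the problem.** The written baseline rule may govern only the 19 prospective patients. The other 21 supply clinical-care forms of unstated timing, so the smaller figures may apply.
- **That conservative patients have several conflicting time origins.** Section 4.5.2 equates study entry with diagnosis, so joining the study, enrolment and diagnosis name essentially one event. Only the wording in 4.3 that counts from treatment is loose, because it has no defined start for these patients.
- **That the power is wrong.** The plan calls its correlation of 0.5 conservative, and step 6 shows only a modest loss if it is lower.

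It is also fair to say that the visit schedule is referred to a flow chart and flow table (Appendices 7 and 8), and that a detailed analysis plan is promised; none of these is shown. They might set a window or choose the baseline record. Even so, 4.5.2a states a positive rule, entry at diagnosis, and would have to agree with them.

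Different origins are partly inherent, since conservative patients have no operation date. Counting both cohorts from study entry would mix different times since surgery, so it is not a clean cure. The comparison is exploratory and unpowered by design. A later baseline would still leave natural change over the post-operative year in the uncontrolled difference.

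**Conclusion.** The point holds in limited form. As written, the primary change score covers the wait plus 12 months, and the text shown provides no means of separating the two. Any mean change before surgery passes into the estimate in full, with unknown sign and size. On assumed drifts of 5 or 10 points, this is 25% or 50% of the target effect if all 40 patients are affected, and about 12% or 24% if only the 19 prospective patients are. The unequal time from baseline touches only the secondary cohort comparison.

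This rests on the text of version 1.2 without Appendices 7 and 8 or an analysis plan. It should be changed because it bears on the primary estimate and the remedy is small. It does not show that the estimate will be materially wrong, and it leaves the sample size of 37 as it is.

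**What to change.** 1. **Section 4.5.2a:** repeat the QLQ-C30 and symptom form shortly before surgery in prospectively recruited surgical patients, within a stated window. Keep the diagnosis form for the baseline comparison of the cohorts.
2. **Section 4.4.4:** name the repeated score as the baseline for the paired t-test.
3. **The 21 earlier patients:** use the last form completed before surgery, report its interval to surgery, and add a sensitivity analysis by interval.
4. **Conservative patients:** use one time origin, study entry (diagnosis), in the synopsis, 3.2.3, 4.3 and 4.5.2, and replace the count from treatment in 4.3.
5. **Cohort comparison:** record completion dates and report the actual time from baseline in each cohort, rather than relying on visit labels.
6. **Appendices 7 and 8:** check that they agree with the revised text.

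The cost is one extra short questionnaire in about 19 patients, plus wording. Section 4.3 already regards the burden of its additional questionnaire surveys as fairly low, though the text shown does not describe a pre-operative visit at which the extra form would be completed, so the occasion must be specified.
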